6.4. Patient Withdrawal

Patients may withdraw from treatment at any time at their own request, or they may be withdrawn at the discretion of the investigator or Sponsor for safety or behavioral reasons, or the inability of the patient to comply with the protocol-required schedule of study visits or procedures at a given study site.

Reasons for discontinuation of study treatment may include:

- Disease progression according to RECIST v. 1.1 ([Appendix 2](#)) and/or irRC ([Appendix 3](#)) (see [Section 5.4.5](#) for details and exceptions);
- Patients who have achieved a confirmed CR, and have had at least two additional cycles of mogamulizumab and PF-05082566 after the date the CR was confirmed;
- Global deterioration of health status requiring discontinuation;
- Unacceptable toxicity;
- Pregnancy;
- Significant protocol violation;
- Lost to follow-up;
- Patient refused further treatment (follow up permitted by the patient);
- Consent withdrawal (cessation of follow up);
- Study terminated by Sponsor;
- Death.

Reasons for withdrawal from study follow-up may include:

- Completed study follow-up;
- Study terminated by Sponsor;

- Start of another anticancer therapy;
- Refusal for further follow-up;
- Lost to follow-up;
- Death.

If a patient does not return for a scheduled visit, every effort should be made to contact the patient. All attempts to contact the patient and information received during contact attempts must be documented in the patient's medical record. In any circumstance, every effort should be made to document patient outcome, if possible. The investigator should inquire about the reason for withdrawal, request the patient return for a final visit, if applicable, and follow-up with the patient regarding any unresolved AEs.

If the patient refuses further visits, no further study specific evaluations should be performed, and no additional data should be collected. The Sponsor may retain and continue to use any data collected before such withdrawal of consent.

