The appearance of any new unequivocal malignant lesion indicates PD. If a new lesion is equivocal, for example due to its small size, continued assessment will clarify the etiology. If repeat assessments confirm the lesion, then progression should be recorded on the date of the initial assessment. A lesion identified in an area not previously scanned will be considered a new lesion.

Supplemental Investigations

If CR determination depends on a residual lesion that decreased in size but did not disappear completely, it is recommended the residual lesion be investigated with biopsy or fine needle aspirate. If no disease is identified, objective status is CR.

If progression determination depends on a lesion with an increase possibly due to necrosis, the lesion may be investigated with biopsy or fine needle aspirate to clarify status.

Objective/Subjective Progression

Patients requiring discontinuation of treatment without objective evidence of disease progression should not be reported as PD on tumor assessment CRFs. This should be indicated on the end of treatment CRF as off treatment due to Global Deterioration of Health Status. Every effort should be made to document objective progression even after discontinuation of treatment.

Table 11. Objective Response Status at each Evaluation

Target Lesions	Non-target Disease	New Lesions	Objective status
CR	CR	No	CR
CR	Non-CR/Non-PD	No	PR
CR	Indeterminate or Missing	No	PR
PR	Non-CR/Non-PD, Indeterminate, or Missing	No	PR
SD	Non-CR/Non-PD, Indeterminate, or Missing	No	Stable
Indeterminate or Missing	Non-PD	No	Indeterminate
PD	Any	Yes or No	PD
Any	PD	Yes or No	PD
Any	Any	Yes	PD

If the protocol allows enrollment of patients with only non-target disease, the following table will be used:

Table 12. Objective Response Status at each Evaluation for Patients with Non Target Disease Only

Non-target Disease	New Lesions	Objective status
CR	No	CR
Non-CR/Non-PD	No	Non-CR/Non-PD
Indeterminate	No	Indeterminate
Unequivocal progression	Yes or No	PD
Any	Yes	PD

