Treatment discontinuation due to 'Disease progression' without documented progression	Not applicable	Information is ignored. Outcome is derived based on documented progression only.
New anti-cancer therapy given	Date of last adequate tumor assessment ^b documenting no PD before new anti-cancer therapy is given or missed tumor assessments	Censored

^a However if the patient dies ≤ 16 weeks after the first dose of study treatment the death is an event with date on death date.

^b If there are no adequate post-baseline assessments prior to PD or death, then the time without adequate assessment should be measured from the first dose of study treatment; if the criteria were met the censoring will be on the 'start date.'

Kaplan-Meier estimates (product-limit estimates) will be presented by treatment group together with a summary of associated statistics including the median PFS time with 2-sided 95% CIs. In particular, the PFS rate at 3, 6, 9, 12 and 15 months will be estimated with corresponding 2-sided 95% CIs. The CIs for the median will be calculated according to Brookmeyer and Crowley and the CIs for the survival function estimates at the time points defined above will be derived using the log-log transformation according to Kalbfleisch and Prentice (conftype=loglog default option in SAS Proc LIFETEST) with back transformation to a CI on the untransformed scale. The estimate of the standard error will be computed using Greenwood's formula.

Frequency (number and percentage) of patients with each event type (PD or death) and censoring reasons will be presented by treatment group. Reasons for censoring will be summarized according to the categories in [Table 4](#) following the hierarchy shown.

Table 4. PFS Censoring Reasons and Hierarchy

Hierarchy	Condition	Censoring Reason
1	No adequate baseline assessment	No adequate baseline assessment
2	Start of new anti-cancer therapy.	Start of new anti-cancer therapy
3	Event after 2 or more missing or inadequate post-baseline tumor assessments/ first dose of study treatment	Event after missing assessments ^a
4	No event and End of study (EOS) = Subject refused further follow-up	Withdrawal of consent
5	No event and lost to follow-up in any disposition page	Lost to follow-up
6	No event and EOS present and no adequate post-baseline tumor assessment	No adequate post-baseline tumor assessment
7	No event and none of the conditions in the prior hierarchy are met	Ongoing without an event

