6.3. Other Endpoints

6.3.1. irRECIST Endpoints

The irRECIST criteria will also be used in this study for exploratory assessments of anti-tumor activity.

The following analyses will be based on the FAS by treatment group based on Investigator assessment.

Immune-related progressive disease (irPD) needs to be confirmed by a second, consecutive assessment at least 4 weeks apart. irPD is also considered to be confirmed if the patient:

- dies within 12 weeks after the initial observation of irPD, or
- discontinues treatment due to disease progression (clinical deterioration without radiological documentation) prior to or within 12 weeks after the assessment of irPD.

Immune-related Best Overall Response (irBOR) will be derived based on reported lesion responses at different evaluation time points from the first dose of study treatment until immune-related disease progression per irRECIST, according to the following rules:

- irCR = at least two determinations of irCR at least 4 weeks apart and before irPD;
- irPR = at least two determinations of irPR or better at least 4 weeks apart and before irPD (and not qualifying for a irCR);
- irSD = at least one irSD assessment (or better) ≥ 6 weeks after the first dose of study treatment and before irPD (and not qualifying for irCR or irPR);
- irPD = at least two consecutive determinations of irPD at least 4 weeks apart;
- irNE: all other cases.

Only tumor assessments performed before the start of any further anti-cancer therapies will be considered in the assessment of irBOR.

Immune-related Objective Response (irOR) is defined as irBOR or irCR or irPR. Immune-related OR rate (irORR) is the proportion of patients with irOR in the analysis set.

Immune-related Duration of Response (irDR) is defined, for patients with an immune-related objective response, as the time from the first documentation of immune-related objective response (irCR or irPR) to the date of first documentation of irPD (which is subsequently confirmed) or death due to any cause. If a patient has not had an event (irPD or death), irDR is censored at the date of last adequate tumor assessment. The censoring rules for irDR are as described below for irPFS.

$$\text{irDR (months)} = [\text{date of event or censoring} - \text{first date of irOR} + 1]/30.4375$$

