Immune-related Time to response (irTTR) is defined, for patients with an irOR, as the time from the first dose of study treatment to the first documentation of immune-related objective tumor response (irCR or irPR) which is subsequently confirmed.

$$\text{irTTR (in months)} = [\text{first date of irOR} - \text{first dose of study treatment} + 1]/30.4375$$

Immune-related Progression-Free Survival (irPFS) is defined as the time from the first dose of study treatment to the date of first irPD (which is subsequently confirmed) or death due to any cause, whichever occurs first. irPFS data will be censored on the date of the last adequate tumor assessment for patients who do not have an event (confirmed irPD or death), for patients who start a new anti-cancer therapy prior to an event or for patients with an event after 2 or more missing tumor assessments. Patients who do not have an adequate baseline tumor assessment or who do not have an adequate post-baseline tumor assessment will be censored on the first dose of study treatment unless death occurred on or before the time of the second planned tumor assessment in which case the death will be considered an event.

The censoring and event date options to be considered for the irPFS and irDR analysis are presented in Table 6.

Table 6. Outcome and Event Date for irPFS and irDR Analyses

Scenario	Date of event/censoring	Outcome
No adequate baseline assessment	first dose of study treatment	Censored ^a
irPD (subsequently confirmed) ^b or death	Date of first irPD or death	Event
- After at most one missing or inadequate post-baseline tumor assessment, OR		
- ≤ 16 weeks after the first dose of study treatment		
irPD (subsequently confirmed) ^b or death after 2 or more missing or inadequate post-baseline tumor assessments	Date of last adequate tumor assessment ^c documenting no irPD before new anti-cancer therapy is given or missed tumor assessments	Censored
Treatment discontinuation due to 'Disease progression' (clinical deterioration without radiological documentation) prior to or within 12 weeks after the assessment of first irPD	Date of first irPD	Event
New anti-cancer therapy prior to confirmed irPD	Date of last adequate tumor assessment ^c documenting no irPD before anti-cancer therapy is given or missed tumor assessments	Censored
(irPD not confirmed or no irPD) and no death	Date of last adequate tumor assessment ^c documenting no irPD before anti-cancer therapy is given or missed tumor assessments	Censored

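### The SAP's clinical route to confirming irPD relies on a discontinuation reason that the protocol does not assign to patients who stop for undocumented deterioration before the irPD scan

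*Protocol*

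**What the plan says.** SAP 6.3.1 confirms irPD by a second consecutive assessment at least 4 weeks later and adds two routes that need no scan. One is that the patient "dies within 12 weeks after the initial observation of irPD, or" the other is that the patient "discontinues treatment due to disease progression (clinical deterioration without radiological documentation) prior to or within 12 weeks after the assessment of irPD". Table 6 repeats the second route as a row of its own, with the event dated at the first irPD: "Treatment discontinuation due to 'Disease progression' (clinical deterioration without radiological documentation) prior to or within 12 weeks after the assessment of first irPD".

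Protocol 6.4 lists two separate reasons for stopping treatment. The first is "Disease progression according to RECIST v. 1.1" and/or irRC. The second is "Global deterioration of health status requiring discontinuation". Appendix 2 (Objective/Subjective Progression) says which patients belong under the second: "Patients requiring discontinuation of treatment without objective evidence of disease progression should not be reported as PD on tumor assessment CRFs". It continues: "This should be indicated on the end of treatment CRF as off treatment due to Global Deterioration of Health Status".

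The SAP text supplied does not mention global deterioration and does not map that code to the irPD rule. SAP Table 3, for RECIST PFS, has a row for "Treatment discontinuation due to 'Disease progression' without documented progression", so the SAP assumes in a second place that the label can be used without documented progression. There the information is ignored, so nothing follows from it.

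**The concern.** The bracketed explanation in the SAP describes a group that the protocol records under a different code. A site that follows Appendix 2 will not enter 'Disease progression' for a patient who deteriorates before any scan shows it, so a derivation that looks for that label will not find the patient.

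The clinical route exists because deteriorating patients are unlikely to return for a second scan. Where it fails, Table 6 treats the irPD as unconfirmed and censors at the last adequate scan without irPD, or at first dose if there was none. That removes an event for a reason related to prognosis, which is informative censoring. The SAP's own wording intends these patients to be events.

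**Working it through.** No figure in the plan is at issue. The check sets the SAP rule, read on its literal label, against the protocol coding for each order of events.

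| Order of events | Reason under the protocol | Literal SAP rule | Result in Table 6 |
|---|---|---|---|
| A. Stops for deterioration with no objective progression; irPD on a later scan | Global deterioration (Appendix 2) | Not met | Censored, unless a second scan or death within 12 weeks confirms |
| B. First irPD scan, then stops with clinical deterioration | 'Disease progression' permitted (6.4) | Met | Event at first irPD |
| C. First irPD scan, then stops on that scan alone | 'Disease progression' permitted (6.4) | Met on the label, although the bracket is not satisfied | Event at first irPD |
| D. First irPD scan, then stops, coded global deterioration | Possible, but not directed by Appendix 2 | Not met | As A |

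Row A is the clear gap. It is the SAP's 'prior to' limb, and it can arise under the protocol. Appendix 2 asks for efforts to document progression after treatment stops, Section 6.2 requires an end-of-treatment tumor assessment if none was done in the previous 8 weeks, and Section 6.3 scans patients without progression every 8 weeks in follow-up.

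The other two routes may not rescue these patients:

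- **Second scan.** Section 5.4.5 makes the repeat scan mandatory only in the absence of clinical deterioration (Section 7.2 says it should be done). Under Section 6.3, a patient who progresses in follow-up is withdrawn and no further data are collected.
- **Death within 12 weeks (84 days) of irPD.** Section 8.2 requires death reporting for 60 days after the last dose. In row A the irPD comes after the last dose, so the 84-day window runs past day 60 and capture is not assured.

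Illustration with two assumed patients, using the SAP formula irPFS = (date − first dose + 1)/30.4375 months:

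1. Week 8 scan irSD; stops at week 14 for deterioration, coded global deterioration; week 16 scan irPD; no further scan; alive.
   - Literal rule: censored at week 8, (56 + 1)/30.4375 = 57/30.4375 = 1.87 months.
   - Code mapped to the rule: event at week 16, (112 + 1)/30.4375 = 113/30.4375 = 3.71 months.
2. Stops at week 6 with the same code; irPD on the first scan at week 8; no further scan; alive.
   - Literal rule: censored at first dose, (0 + 1)/30.4375 = 0.03 months.
   - Code mapped to the rule: event at week 8, 57/30.4375 = 1.87 months.

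In each case an event becomes a censored time. Row C works the other way: a single unconfirmed scan is counted as a confirmed event.

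**The case against.** The strongest reply is that Appendix 2 is limited to stops without objective evidence of progression. Every patient whom the irPD rule can reach has an irPD scan at some point. Growth of at least 20% or a new lesion on that scan is normally also RECIST PD (apart from growth of less than 5 mm in absolute terms), so a stop after it may properly be coded 'Disease progression'. This stands. A reader might infer that the two documents assign the codes the opposite way round, and that the rule fails for deteriorating patients as a class; they do not, because rows B and C are captured.

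Death within 12 weeks and a second scan confirm irPD whatever the code. This also stands in principle, with the limits on follow-up shown above.

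The SAP's bracket could be read as already covering global deterioration. Neither the end-of-treatment CRF nor the programming specification is supplied, and the SAP amendment history says that edits were made to match data collection. So a miss is possible and not demonstrated. But the SAP names one label and never the other, and two programmers could derive different events from it.

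Finally, global deterioration is not confined to tumor-related decline, and Protocol Appendix 3 confirms irPD by imaging only. Adding the code without limits would widen an existing departure from the protocol. This is a fair constraint on the fix.

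**Conclusion.** The point holds for the 'prior to' limb. Read on the stated label, the rule does not confirm irPD in patients who stop for undocumented deterioration, show irPD later, and have neither a second scan nor a death within 12 weeks. A stop after irPD that happens to be coded global deterioration would be missed in the same way.

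How many patients this affects cannot be computed from the documents. A reader might assume that a sizeable share of all patients with irPD at the first scan would drop out of the event count. That is not supported. Each such patient would have to stop before about week 8, be coded global deterioration, still be scanned, have no second scan and survive 12 weeks.

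A reader might also infer that irPFS is inflated overall. Row A raises the curve and row C lowers it, so the net direction is not established.

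The reach is limited to irPFS and irDR. SAP 3.2.2 lists them with the secondary efficacy endpoints for expansion cohorts only; SAP 6.3.1 calls the irRECIST assessments exploratory. RECIST PFS and DR ignore the discontinuation reason, an irBOR of irPD requires two determinations, and the DLT and MTD analyses are untouched. The conclusion assumes that sites code as Appendix 2 instructs and that the derivation uses the literal label. It is still worth correcting, because the rule as worded misses patients whom its own bracket intends to count.

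**What to change.** In SAP 6.3.1 and Table 6:

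- Name the end-of-treatment reasons that count as clinical confirmation of irPD. Include global deterioration of health status when no objective progression had been documented at the stop, within a stated window. The SAP gives 12 weeks after the irPD scan but no limit before it; state one.
- Say whether a stop based only on the first irPD scan counts as clinical confirmation.
- Report irPD events by route: second scan, death, clinical discontinuation.
- State that the clinical route departs from the imaging-only confirmation in Protocol Appendix 3, and give irPFS and irDR without that route as a sensitivity analysis.

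The use of the two discontinuation reasons in Protocol 6.4, Protocol Appendix 2 and the SAP should be reconciled.

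The cost is a short SAP edit and a small programming change, with no new data collection. The downside is that some deterioration not caused by the tumor may be counted as confirmation. The condition on documented progression, the window and the sensitivity analysis limit that risk and make it visible.

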Appendix 3. Immune-related Response Criteria Derived from RECIST 1.1 (irRECIST)

Increasing clinical experience indicates that traditional response criteria may not be sufficient to fully characterize activity in this new era of targeted therapies and/or biologics.

This is particularly true for immunotherapeutic agents such as anti-CTLA4 and anti-PD1\anti-PDL1 which exert the antitumor activity by augmenting activation and proliferation of T cells, thus leading to tumor infiltration by T cells and tumor regression rather than direct cytotoxic effects.^{34, 35} Clinical observations of patients with advanced melanoma treated with ipilimumab, for example, suggested that conventional response assessment criteria such as RECIST and WHO criteria are not sufficient to fully characterize patterns of tumor response to immunotherapy because tumors treated with immunotherapeutic agents may show additional response patterns that are not described in these conventional criteria.^{36, 37}

Furthermore, the conventional tumor assessment criteria (RECIST and WHO criteria) have been reported as not capturing the existence of a subset of patients who have an OS similar to those who have experienced CR or PR but were flagged as PD by WHO criteria.^{36, 37}

On these grounds, a tumor assessment system has been developed that incorporates these delayed or flare-type responses into the RECIST 1.1 criteria (irRECIST).³⁸

For irRECIST, only target and new measurable lesions are taken into account. In contrast to the RECIST 1.1, the irRECIST criteria:

- Require confirmation of both progression and response by imaging at least 4 weeks from the date first documented, and
- Does not necessarily score the appearance of new lesions as progressive disease if the sum of lesion diameters of target lesions (minimum of 10 mm longest diameter per non-nodal lesion and 15 mm shortest diameter per nodal lesion, maximum of 5 target lesions, maximum of 2 per organ) and measurable new lesions does not increase by $\geq 20\%$.

The same method of assessment and the same technique should be used to characterize each identified and reported target lesion(s) at baseline and throughout the trial.

irRECIST criteria are defined as follows:

- Overall immune-related complete response (irCR): Complete disappearance of all lesions (whether measurable or not) and no new lesions. All measurable lymph nodes also must have a reduction in short axis to <10 mm.
- Overall immune-related partial response (irPR): Sum of the diameters (longest for non-nodal lesions, shortest for nodal lesions) of target and new measurable lesions decreases $\geq 30\%$.

- Overall immune-related stable disease (irSD): Sum of the diameters (longest for non-nodal lesions, shortest for nodal lesions) of target and new measurable lesions is neither irCR, irPR, (compared to baseline) or immune-related progressive disease (irPD, compared to nadir).
- Overall immune-related progressive disease (irPD): Sum of the diameters (longest for non-nodal lesions, shortest for nodal lesions) of target and new measurable lesions increases $\geq 20\%$ (compared to nadir), confirmed by a repeat, consecutive observation at least 4 weeks from the date first documented.

New measurable lesions: Incorporated into tumor burden (ie, added to the target lesion measurements). A lymph node has to be ≥ 15 mm in short axis to be a measurable new lesion and its short axis measurement is included in the sum. Up to 2 new lesions per organ and up to 5 new lesions in total can be added to the measurements.

New non-measurable lesions: Do not define progression but preclude irCR.

Overall responses derived from changes in target, non-target, and new lesions are outlined in Table 13.

Table 13. Overall Response Derived from Changes in Target, Non-target and New Lesions

Measurable response Target and New Measurable Lesions (Tumor Burden) ^a	Non-measurable response		Overall response using irRECIST ^b
	Non-Target Lesions	New Non-Measurable Lesions	
Decrease 100%	Absent	Absent	irCR
Decrease 100%	Stable	Any	irPR
Decrease 100%	Unequivocal progression	Any	irPR
Decrease $\geq 30\%$	Absent/stable	Any	irPR
Decrease $\geq 30\%$	Unequivocal progression	Any	irPR
Decrease $< 30\%$ and increase $< 20\%$	Absent/stable	Any	irSD
Decrease $< 30\%$ and increase $< 20\%$	Unequivocal progression	Any	irSD
Increase $\geq 20\%$	Any	Any	irPD

a. Decrease assessed relative to baseline.

b. Response (irCR and irPR) and progression (irPD) must be confirmed by a second, consecutive assessment at least 4 weeks apart.

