All sites of disease must be assessed at baseline. Baseline assessments should be done as close as possible prior to study start. For an adequate baseline assessment, all required scans must be done within 28 days prior to treatment and all disease must be documented appropriately. If baseline assessment is inadequate, subsequent statuses generally should be indeterminate.

Target lesions

All measurable lesions up to a maximum of 2 lesions per organ, 5 lesions in total, representative of all involved organs, should be identified as target lesions at baseline. Target lesions should be selected on the basis of size (longest lesions) and suitability for accurate repeated measurements. Record the longest diameter for each lesion, except in the case of pathological lymph nodes for which the short axis should be recorded. The sum of the diameters (longest for non-nodal lesions, short axis for nodal lesions) for all target lesions at baseline will be the basis for comparison to assessments performed on study.

If two target lesions coalesce the measurement of the coalesced mass is used. If a large target lesion splits, the sum of the parts is used.

Measurements for target lesions that become small should continue to be recorded. If a target lesion becomes too small to measure, 0 mm should be recorded if the lesion is considered to have disappeared; otherwise a default value of 5 mm should be recorded.

NOTE: When nodal lesions decrease to <10 mm (normal), the actual measurement should still be recorded.

Non-target disease

All non-measurable disease is non-target. All measurable lesions not identified as target lesions are also included as non-target disease. Measurements are not required but rather assessments will be expressed as ABSENT, INDETERMINATE, PRESENT/NOT INCREASED, INCREASED. Multiple non-target lesions in one organ may be recorded as a single item on the case report form (eg, 'multiple enlarged pelvic lymph nodes' or 'multiple liver metastases').

OBJECTIVE RESPONSE STATUS AT EACH EVALUATION

Disease sites must be assessed using the same technique as baseline, including consistent administration of contrast and timing of scanning. If a change needs to be made the case must be discussed with the radiologist to determine if substitution is possible. If not, subsequent objective statuses are indeterminate.

Target disease

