- Complete Response (CR): Complete disappearance of all target lesions with the exception of nodal disease. All target nodes must decrease to normal size (short axis <10 mm). All target lesions must be assessed.
- Partial Response (PR): Greater than or equal to 30% decrease under baseline of the sum of diameters of all target measurable lesions. The short diameter is used in the sum for target nodes, while the longest diameter is used in the sum for all other target lesions. All target lesions must be assessed.
- Stable: Does not qualify for CR, PR or Progression. All target lesions must be assessed. Stable can follow PR only in the rare case that the sum increases by less than 20% from the nadir, but enough that a previously documented 30% decrease no longer holds.
- Objective Progression (PD): 20% increase in the sum of diameters of target measurable lesions above the smallest sum observed (over baseline if no decrease in the sum is observed during therapy), with a minimum absolute increase of 5 mm.
- Indeterminate. Progression has not been documented, and
 - One or more target measurable lesions have not been assessed;
or
 - Assessment methods used were inconsistent with those used at baseline;
or
 - One or more target lesions cannot be measured accurately (eg, poorly visible unless due to being too small to measure);
or
 - One or more target lesions were excised or irradiated and have not reappeared or increased.

Non-target disease

- CR: Disappearance of all non-target lesions and normalization of tumor marker levels. All lymph nodes must be 'normal' in size (<10 mm short axis).
- Non-CR/Non-PD: Persistence of any non-target lesions and/or tumor marker level above the normal limits.

- PD: Unequivocal progression of pre-existing lesions. Generally the overall tumor burden must increase sufficiently to merit discontinuation of therapy. In the presence of SD or PR in target disease, progression due to unequivocal increase in non-target disease should be rare.
- Indeterminate: Progression has not been determined and one or more non-target sites were not assessed or assessment methods were inconsistent with those used at baseline.

New Lesions

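### Protocol Appendix 3 contradicts itself on irCR for normalised nodes, omits RECIST's 5 mm minimum from irPD without saying so, and does not rank the rows of Table 13

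*Protocol*

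**What the plan says.** **irCR.** The definition in Protocol Appendix 3 requires all lesions to disappear, with a separate rule for nodes: "All measurable lymph nodes also must have a reduction in short axis to <10 mm". The appendix then says "Overall responses derived from changes in target, non-target, and new lesions are outlined in Table 13". In that table the only irCR row requires a 100% decrease in the combined target and new measurable burden, with non-target and new non-measurable lesions absent. Nodal short axes are part of that burden. On recording, Appendix 2 notes: "When nodal lesions decrease to <10 mm (normal), the actual measurement should still be recorded".

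**irPD.** Appendix 3 words it as "Overall immune-related progressive disease (irPD): Sum of the diameters (longest for non-nodal lesions, shortest for nodal lesions) of target and new measurable lesions increases" by 20% or more, "compared to nadir), confirmed by a repeat, consecutive observation at least 4 weeks from the date first documented". The last row of Table 13 repeats the 20% with no millimetre condition. RECIST progression in Appendix 2 has the same 20%, but "with a minimum absolute increase of 5 mm".

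**Stated differences.** After "In contrast to the RECIST 1.1, the irRECIST criteria", Appendix 3 gives two bullets: confirmation of response and progression, and the handling of new lesions.

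**Reference points.** Table 13, note a, says "Decrease assessed relative to baseline". The irPD definition measures the increase from nadir.

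**SAP.** Section 6.3.1 builds irBOR from counts of irCR, irPR, irSD and irPD determinations. Neither it nor Section 3.2.2 adds a 5 mm condition, resolves the nodal conflict or ranks the rows.

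**The concern.** Three gaps leave the immune-related status of some patients undetermined or unexpectedly strict.

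- A patient with normalised target nodes gets one category from the definition and another from the table.
- Criteria adopted to accommodate delayed or flare-type responses can call progression earlier than RECIST does when the tumour burden is small. The reader cannot tell whether that was intended.
- A deep responder whose sum rises modestly from nadir can be filed under two rows at once.

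The first gap shifts irBOR between irCR and irPR; it leaves irORR alone, because both count as response. The second and third can change irBOR and irORR, by deciding whether a second irPR determination comes before irPD. They also decide who has an irTTR, and they move event dates for irDR and irPFS. The patients most exposed are good responders and those with small disease, because their nadir sums are small.

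**Working it through.** The plan gives no figure to reproduce, so the check is arithmetic on the thresholds. Lesion sizes are illustrative.

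**1. irCR: text against table**

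Inputs: a measurable node is at least 15 mm in short axis at baseline (Appendices 2 and 3), a normalised node is below 10 mm, and its actual size stays in the sum.

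Percent decrease = 100 × (1 − follow-up sum / baseline sum).

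| Case | Baseline to follow-up (mm) | Decrease | By irCR text | By Table 13 |
|---|---|---|---|---|
| One node | 15 to 9 | 1 − 9/15 = 40.0% | irCR | irPR |
| Two nodes | 20 + 15 to 9 + 8 | 1 − 17/35 = 51.4% | irCR | irPR |
| Non-nodal lesion plus node | 30 + 15 to 0 + 9 | 1 − 9/45 = 80.0% | irCR | irPR |
| Node judged gone | 15 to 0 | 100% | irCR | irCR |

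All rows assume that non-target disease and new lesions are absent. The result is general. If each target node goes from at least 15 mm to below 10 mm and the rest vanishes, the decrease exceeds 1 − 10/15 = 33.3%. Table 13 then always gives irPR unless every node is recorded as 0 mm. The first three cases are also CR under Appendix 2, which accepts target nodes of normal size.

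**2. irPD: effect of the missing minimum**

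Increase needed for irPD = 0.20 × nadir. Increase needed for RECIST PD = max(0.20 × nadir, 5 mm). The two agree once 0.20 × nadir reaches 5 mm, that is, at a nadir of 5/0.20 = 25 mm.

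| Nadir sum (mm) | irPD needs (mm) | RECIST PD needs (mm) |
|---|---|---|
| 5 | 1.0 | 5.0 |
| 10 | 2.0 | 5.0 |
| 12 | 2.4 | 5.0 |
| 15 | 3.0 | 5.0 |
| 20 | 4.0 | 5.0 |
| 25 | 5.0 | 5.0 |
| 50 | 10.0 | 10.0 |

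Confirmation does not remove the difference. Take 20 mm at baseline, 12 mm at nadir (a 40% decrease), then 15 mm, and still 15 mm at a repeat scan at least 4 weeks later. The rise is (15 − 12)/12 = 25% on both scans, so irPD is confirmed. The absolute rise is 3 mm, so RECIST records no PD.

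Such nadirs are attainable. A baseline sum of 35 mm that falls by 30% gives 24.5 mm.

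**3. Row precedence**

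For 50 to 10 to 12 mm, the decrease from baseline is 1 − 12/50 = 76%, which fits the irPR row. The increase from nadir is 12/10 − 1 = 20%, which fits the irPD row. The irSD definition already excludes irPD, but nothing ranks irPR against irPD.

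Adding the 5 mm minimum would not settle this. At 10 + 5 = 15 mm the patient is 70% below baseline and 50% above nadir, and again fits both rows.

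The same overlap exists between irCR and irPD. A lone node going from 8 to 9.7 mm stays below 10 mm, so it still meets the nodal rule, yet it has risen by 1.7/8 = 21%. With a 5 mm minimum the overlap shrinks but does not vanish: a lone node with a nadir below 5 mm can rise by 5 mm and remain below 10 mm.

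**The case against.** **The definition governs and the table only summarises it.** Appendix 3 introduces the written criteria as the definitions and describes Table 13 as an outline. A reader might infer that patients with nodal disease cannot reach irCR. The documents do not support that: the definition allows it, and a node recorded as 0 mm meets even the table's 100%. This stands. What remains is a disagreement between text and table, with no statement of which one applies.

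**The missing minimum may be a choice.** irRECIST comes from a cited source that cannot be consulted here, so it cannot be said that a minimum was dropped from it. Nor are the two contrast bullets stated to be exhaustive. Table 13 also lets unequivocal non-target progression stay irPR or irSD, which neither bullet mentions. This stands too, and it is why declaring the difference is an acceptable remedy.

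**Small changes do not simply become irPD.** A reader might infer that any small increase counts as progression. It does so only at nadir sums below 25 mm, only for rises of at least 20% but under 5 mm, and only when confirmed by a repeat scan or by the substitutes in SAP Section 6.3.1 (death, or discontinuation for progression, within its time limits). At a nadir of 20 mm the window is 4.0 to just under 5.0 mm.

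**The stakes are modest.** SAP Section 6.3.1 calls irRECIST exploratory, SAP Section 5.1.1 plans no hypothesis test, and Protocol Section 5.4.5 lets treatment continue after confirmed progression where there is clinical benefit. This mostly stands. However, SAP Section 3.2.2 lists the immune-related endpoints under secondary efficacy, and Protocol Section 2.2 refers the secondary response endpoint to Appendix 3.

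**Conclusion.** The point holds in three limited parts.

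1. The irCR definition and Table 13 disagree for every patient who meets the definition while a target node still has a non-zero recorded size.
2. irPD lacks the 5 mm minimum of Appendix 2, and this is not declared. The two rules differ only below a 25 mm nadir sum, and the gap widens as the nadir falls (1 mm at a nadir of 20 mm, 3 mm at 10 mm).
3. Table 13 gives two answers for some patients and does not say which one counts.

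This rests on reading Appendix 2's note on recording normalised nodes as applying to the irRECIST sum, and on reading the irPD definition as complete in itself. Appendix 3 states no other recording rule. Its irPD definition has its own threshold and does not refer back to Appendix 2.

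The documents give no basis for estimating how many patients would be affected. The effect is confined to the descriptive irBOR, irORR, irDR, irTTR and irPFS. The DLT primary endpoint and the RECIST 1.1 analyses are unaffected. A reader might also infer that patients would be taken off treatment wrongly. The documents do not show that, since progression is one possible reason for stopping and Protocol Section 5.4.5 allows exceptions.

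**What to change.** For deriving the immune-related endpoints, amend Appendix 3 as follows and refer to it from SAP Section 6.3.1:

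1. **irCR row of Table 13.** Replace the 100% decrease with the condition in the text: every non-nodal lesion gone and every measurable node under 10 mm short axis, with non-target and new lesions absent.
2. **irPD.** Apply the 5 mm minimum of Appendix 2 in both the definition and the last row of Table 13, or list its absence as a further difference from RECIST 1.1.
3. **Precedence.** State that the irPD row, judged against nadir, overrides the irPR and irSD rows, and that a patient who still meets irCR by the nodal rule is not irPD.

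Protocol Sections 5.4.4 and 6.4, which cite progression by irRC as a ground for ending treatment, must be reconciled with whichever definition the sponsor adopts.

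The cost is a few lines of text, with no new scans or measurements. Status can be re-derived from recorded diameters where scans exist, with two limits. SAP Section 6.3.1 works from investigator-reported responses, so a derivation step would be needed. Protocol Section 6.3 ends data collection once progression is shown in follow-up, so some later scans may be missing.
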